4.3. Subject Study Withdrawal Criteria

Subjects who do not receive all study drug doses in the main study are encouraged to remain in the study and continue with the regular study visits and assessments. However, subjects may withdraw from the study at any time, for any reason. Reasons for discontinuing study drug treatment, as well as reasons for withdrawing from study, will be captured on CRF.

Mandatory reasons for withdrawing the subject from the study include the following:

- Any safety concern in the Investigator's opinion, that precludes further study participation, including infusion-associated reactions deemed life-threatening by the Investigator (see also/ Section 5.1.6)
- Lung transplant
- Pregnancy
- Major protocol deviation that substantially affects subject safety or assessment of efficacy endpoints
- Withdrawal of Consent

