4.4. Subject Study Withdrawal Procedures/Assessments

Subjects who terminate / withdraw from the study early, for any reason, will have an Early Study Termination (ET) visit as soon as feasible. Study procedures to be performed during the ET visit can be found in the SOA (Appendix 1). At the ET visit, PFTs and questionnaires do not have to be repeated, if the last one (excluding screening visit) was performed within 8 weeks of this visit; HRCT does not have to be repeated, if the last one (excluding the screening visit) was performed within 4 months of this visit.

These subjects will have a safety follow-up visit 28 days after the last dose. A follow-up phone call 60 days after last dose will also be completed for a final assessment of safety.

In addition, these subjects should be contacted by phone for vital status at weeks 24 and 48. These subjects will not be eligible for the OLE phase.

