8.3.4.1. Primary Endpoint Analysis

The primary estimand is intended to provide a population level estimate of the treatment effects of the pamrevlumab on a continuous endpoint, regardless of participants compliance with the IP dosing. Under an estimand framework, the analysis of primary endpoint includes the following components:

Population: Male and female patients aged 40 to 85 years, inclusive at screening initiation with IPF diagnosis made within 7 years prior to screening under American Thoracic Society/European Respiratory Society (ATS/ERS) criteria (Raghu 2018), and not currently receiving treatment with the 2 approved antifibrotic standard of care medications. All subjects in ITT population will be included.

Endpoint: Change from baseline in FVC (L) assessment at Week 48.

Treatment of interest: The randomization study treatment (pamrevlumab or placebo).

Handling of intercurrent events: The treatment policy strategy will be adopted for primary analysis. Details on handling missing values will be defined in a Statistical Analysis Plan (SAP).

Population-level summary for the endpoint: Absolute LSMMeans difference between pamrevlumab and placebo in change from baseline to Week 48 in FVC (L) estimated from a random coefficient model (RCM), the primary analysis approach. RCM model includes treatment, visit (as a continuous variable), visit-by-treatment interaction, randomization stratification factor, baseline FVC volume, age, sex, height as fixed effects, and the intercept and linear slope of visit as random effects. Details of RCM model will be defined in the SAP.

Additional sensitivity and supplemental analyses on primary endpoint will be defined in the SAP. The following analysis will be performed including, but not limited to:

1. With alternative model using quadratic assumption of FVC decline
2. Alternative assumptions for missing data (imputation method):
 - a. Missing not at random: Pattern mixture model (e.g., control-based imputation)
 - b. Missing not at random: Tipping point analysis (e.g., delta-adjusting pattern imputation)

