6.2. Important Protocol Deviations

The number and percentage of subjects with important protocol deviations will be categorized and tabulated as appropriate for the ITT population. COVID-19-related important protocol deviations will be summarized in a separate table. All protocol deviations will be finalized prior to unblinding.

A subset of pre-specified major protocol deviations will exclude some patients in the PPS analyses if these deviations significantly impact efficacy analyses. These major PDs will be reviewed and finalized by following FibroGen medical review process prior to database lock and unblinding. Considerations will be given according to the following table.

Confidential Page 20 of 56

Number	Major Protocol Deviation
1	Violation of any inclusion or exclusion criteria that may affect the assessment of
	efficacy or safety of the study drug*
2	Withdrawal Deviation: Subject met withdrawal criteria during the study but was
	not withdrawn*
3	Dosing Deviation: Subject received the wrong treatment or incorrect dose,
	including incorrect timing of a dose, which may affect the assessment of efficacy
	or safety of the study drug*
4	Administration of prohibited concomitant medication that may impact evaluation
	of efficacy of the study drug*
5	Significant noncompliance with study procedures that may impact evaluation of
	efficacy of the study drug will be evaluated case by case*

Table 1: Criteria for Major Protocol Deviations

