6.7.1.1.3. Intercurrent Event Handling Strategy

Treatment discontinuation due to non-death reasons: Treatment policy strategy will be used. Missing data are assumed to be missing at random.

Confidential Page 24 of 56

Death: Post-death FVC values will be set as the worst (lowest) post-baseline FVC values across all randomized subjects in the double-blind period. Missing study day will be imputed as the target day of each analysis visit.

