6.7.1.2.2. Jump-to-Control Analysis

The goal of the jump-to-control analysis is to address the possibility of data being missing not at random (MNAR). The missing data pattern for the pamrevlumab subjects after withdrawal from the study can be assumed to switch to the same data pattern as subjects on the placebo treatment. Subjects that discontinued from the placebo arm are assumed to have the same data pattern as placebo subjects that remain in the study (excluding post-death missing values defined in Section 6.7.1.1.3). This is often called the jump-to-control approach.

The analysis of covariance (ANCOVA) model will contain terms for treatment, baseline FVC measurements, covariates (age, sex, race group, and height), and the randomization stratification factor (Example SAS code in Appendix 7.2).

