6.7.1.2.3. Delta-Adjusting (Tipping Point) Analysis

An alternative assumption is that the missing data for the pamrevlumab treated subjects who discontinue early have a lower expected value than the pamrevlumab subjects remaining in the study, while subjects who discontinue from the placebo arm are assumed to have the same data pattern as placebo subjects remaining in the study (excluding post-death missing values defined in Section 6.7.1.1.3). This is often called the delta-adjusting (or tipping point) approach (Example SAS code in Appendix 7.3).

ANCOVA will be performed as Section 6.7.1.2.2.

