6.7.2.1.3. Intercurrent Event Handling Strategy

Treatment discontinuation (such as early termination due to AEs, Lost to Follow-Up, Withdrawal by Subject, Physician Decision, Protocol Deviations, etc.): Treatment policy strategy will be used.

Death: Composite strategy will be used if death is a component of the endpoint.

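### Mandatory study withdrawal for deviations that affect efficacy assessment stops FVC collection that the treatment-policy primary analysis needs to Week 48

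*Protocol*

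**What the plan says.** **Withdrawal rule.** Protocol Section 4.3 first encourages subjects who miss doses to stay for visits. It then lists mandatory reasons for withdrawal from the study, among them "Major protocol deviation that substantially affects subject safety or assessment of efficacy endpoints". Neither 'major' nor 'substantially' is defined there.

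**What follows withdrawal.** Sections 4.4 and 6.1.4 provide an early termination (ET) visit, a safety visit 28 days and a call 60 days after the last dose, and vital-status calls at Weeks 24 and 48. No spirometry is scheduled after the ET visit. Even at that visit, per Section 4.4, "PFTs and questionnaires do not have to be repeated, if the last one (excluding screening visit) was performed within 8 weeks of this visit".

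**Deviation table.** SAP Section 6.2, Table 1, item 2 lists as a major deviation "Withdrawal Deviation: Subject met withdrawal criteria during the study but was" not withdrawn.

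**Primary estimand.** Protocol Section 8.3.4.1 aims at the treatment effect "regardless of participants compliance with the IP dosing", by treatment policy in the ITT population of all randomized subjects. SAP Section 6.7.1.1.4 uses FVC to Week 48, including values available after treatment stops. SAP Section 6.7.1.1.3 adds: "Missing data are assumed to be missing at random".

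**Time-to-event secondaries.** SAP Section 6.7.2.1.3 gives a list of early-termination reasons that ends "Protocol Deviations, etc.): Treatment policy strategy will be used".

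**The concern.** One rule ends collection of the data that another rule needs. A treatment-policy analysis gains its credibility from observed FVC in subjects whose conduct departed from plan. The efficacy limb removes some of those subjects from follow-up because of that departure. Their later FVC is then supplied by a missing-at-random model, although they left for a reason tied to events after randomization.

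The loss is also unnecessary. A deviation that spoils the assessment of efficacy can be handled at analysis, by excluding the subject from the per-protocol set (SAP Sections 5.2.2 and 6.7.1.3.2). Data can be excluded later, but values that were never collected cannot be recovered. Because the trigger terms are undefined, sites may also apply the rule unevenly.

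At stake are the completeness of the primary endpoint and a possible small bias in it. Time to disease progression also loses follow-up, because SAP Section 6.7.2.1.4.1 censors event-free subjects at their last PFT.

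**Working it through.** **1. Sample size (Protocol Section 8.1; SAP Section 3.2).** Inputs: difference 120 mL, SD 300 mL, two-sided alpha 0.05, power at least 90%, dropout about 20%, N = 340 (170 per arm).

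- Normal approximation: n per arm = 2 × (1.960 + 1.282)² × (300/120)² ≈ 131.4, rounded up to 132. Total 264; 264/0.8 = 330.
- Noncentral t: 133 per arm, total 266; 266/0.8 = 332.5.
- With the full 20% lost, 340 × 0.8 = 272, or 136 per arm. Power is 90.8% (noncentral t).

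The planned 340 is sound. Withdrawals that fall inside the 20% allowance leave the stated power intact.

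**2. Who is affected.** Missed doses (Section 4.3) and approved IPF therapy (Section 5.1.10) are already followed within the study. The limb reaches only a residual group, whose size is not given.

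**3. Possible shift in the estimate.** If a fraction *w* of one arm is withdrawn and their true mean Week 48 FVC differs by *g* mL from the missing-at-random prediction, the arm mean shifts by *w × g*. Both inputs are assumptions: *w* from 1% to 5% (1.7 to 8.5 of 170 subjects), *g* from 50 to 150 mL. The standard error is 300 × √(2/136) = 36.4 mL.

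| *w* | *g* (mL) | Shift (mL) | In SE | Share of 120 mL |
|---|---|---|---|---|
| 1% | 50 | 0.5 | 0.01 | 0.4% |
| 3% | 50 | 1.5 | 0.04 | 1.25% |
| 3% | 150 | 4.5 | 0.12 | 3.75% |
| 5% | 150 | 7.5 | 0.21 | 6.25% |

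If both arms are affected, the net shift is the difference of the two products. At 4% versus 2% with 150 mL in each, it is 6 − 3 = 3 mL, or 0.08 SE. At equal rates and equal gaps it is 0.

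**4. Does the ET visit fill the gap?** Only in part. The Week 48 PFT window opens on Day 296 (SAP Appendix 2, Table 7), so a late ET spirometry can count as Week 48. But after a Week 36 PFT on Day 253 the waiver runs to Day 253 + 56 = Day 309. On Days 296 to 309 (14 days) an ET visit could supply a Week 48 value but need not. With the Week 36 visit 7 days early or late, the overlap is 7 or 21 days.

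**5. Do the sensitivity analyses cover it?** Also in part. Under jump-to-control, "Subjects that discontinued from the placebo arm are assumed to have the same data pattern as placebo subjects that remain in the study"; under the tipping-point analysis, "subjects who discontinue from the placebo arm are assumed to have the same data pattern as placebo subjects remaining in the study". Both vary the assumption for pamrevlumab withdrawals only. The ranked ANCOVA (SAP Section 6.7.1.2.4) imputes missing Week 48 values in both arms from subjects with similar trajectories. All three replace the missing values by assumption.

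**The case against.** The strongest reply is that the estimand is not contradicted. Treatment policy is stated for compliance and treatment discontinuation, and the SAP uses values that are available after it. Leaving the study is a missing-data matter, handled by the missing-at-random assumption and then by the sensitivity analyses. This is fair as a reading of the text, and the point is best seen as a design choice. It does not remove the fact that the protocol itself causes the missingness.

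Other parts of the reply also stand:

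- SAP Table 1 item 2 bears on the supplemental per-protocol set only. A subject kept in the study still counts in the primary analysis, so item 2 adds little penalty.
- The mention of protocol deviations in SAP Section 6.7.2.1.3 sits in a generic list, beside reasons after which FVC usually cannot be obtained. It does not show that the SAP expected continued spirometry. Censoring at the last PFT applies to every event-free subject.
- The ET waiver applies to all early terminations and does not forbid the test.
- Keeping placebo dropouts on the placebo pattern is the normal jump-to-control design.
- Rates and gaps are assumed. Sites are blinded, so the arms may be affected alike and the net shift may be close to zero.
- Some deviations, such as a wrong dose, may touch both safety and efficacy, so the two limbs do not always separate cleanly.

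These points limit the size and certainty of the harm. None of them recovers the FVC values that are not collected.

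**Conclusion.** The concern holds. Following Section 4.3 as written stops scheduled FVC collection in randomized subjects whose Week 48 value the primary analysis calls for, and no analysis in the plan requires that. The effect is probably small: 0.5 to 7.5 mL if one arm alone is affected, under the assumed 1% to 5% and 50 to 150 mL, and nearer zero if the arms are balanced. Its direction is unknown. The sample size and stated power are not in question. The change is worth making because the missingness is avoidable and conduct-related, in the primary endpoint, and cheap to prevent. Confidence is moderate, because the documents do not show how many subjects the limb would reach.

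**What to change.** - **Protocol Section 4.3:** remove the limb on efficacy assessment from the mandatory study-withdrawal list. State that such deviations are recorded and handled through the per-protocol supplemental analysis, and that scheduled PFT, HRCT, questionnaire, event and vital-status collection continues while consent remains.
- **SAP Table 1, item 2:** reword so that keeping these subjects in the study is not itself a deviation. Retain it for the other withdrawal criteria.
- **Left alone:** the safety limb, the other mandatory reasons and every decision about study drug remain with the clinical team. A deviation touching both limbs would still be judged under the safety limb.

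The cost is a protocol amendment with IRB/IEC approval (Protocol Section 10.2) across approximately 170 planned sites, best bundled with another amendment, plus a small SAP wording change. A few subjects would attend visits they would otherwise have missed. The sample size does not change.

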4.4. Subject Study Withdrawal Procedures/Assessments

Subjects who terminate / withdraw from the study early, for any reason, will have an Early Study Termination (ET) visit as soon as feasible. Study procedures to be performed during the ET visit can be found in the SOA (Appendix 1). At the ET visit, PFTs and questionnaires do not have to be repeated, if the last one (excluding screening visit) was performed within 8 weeks of this visit; HRCT does not have to be repeated, if the last one (excluding the screening visit) was performed within 4 months of this visit.

These subjects will have a safety follow-up visit 28 days after the last dose. A follow-up phone call 60 days after last dose will also be completed for a final assessment of safety.

In addition, these subjects should be contacted by phone for vital status at weeks 24 and 48. These subjects will not be eligible for the OLE phase.

4.5. Replacement of Study Subjects

All randomized subjects will be included in the study. Subjects who terminate the study early will not be replaced.

4.6. Study Closure

FibroGen reserves the right to close any investigational site(s) or terminate the study at any time for any reason. Reasons for the closure of the study site or termination of the study by FibroGen may include (but are not limited to):

- Successful completion of the study at the investigational site
- The required number of subjects for the study has been recruited
- Failure of the Investigator to comply with the protocol, GCP guidelines or local requirements
- Safety concerns
- Inadequate recruitment of subjects by the Investigator

5. TREATMENT OF SUBJECTS

5.1. Study Treatment

5.1.1. Pamrevlumab or Placebo

Pamrevlumab is a fully human IgG1 kappa monoclonal antibody that binds to CTGF and is formulated as solution for administration by IV infusion.

Matching placebo is formulated as solution to be administered in a manner that is identical to pamrevlumab infusion.

5.1.2. Formulation

Pamrevlumab is supplied in single-use glass vials containing sterile, preservative-free solution (100 mg pamrevlumab/vial or 500 mg pamrevlumab/vial respectively). The solution is composed of 10 mg/mL pamrevlumab, 1.60 mg/mL L-histidine, 3.08 mg/mL L-histidine HCl, 8.01 mg/mL sodium chloride, and 0.05 mg/mL polysorbate 20, resulting in a solution with a tonicity of approximately 290 mmol/kg and a pH of 6.0.

The placebo formulation is of identical composition as the pamrevlumab formulation, except for the absence of pamrevlumab.

5.1.3. Study Drug Packaging and Labeling

Labels will be prepared and will comply with Good Manufacturing Practice requirements for labelling and local regulatory guidelines.

5.1.4. Study Drug Storage

All Investigational Product (IP) vials must be stored refrigerated (2°C to 8°C), in a temperature-controlled and monitored environment, protected from light, and in a securely locked area to which access is limited to appropriate study personnel. Documentation of the storage conditions must be maintained by the site for the entire period of study participation. Details regarding the reporting of temperature excursions can be found in the study Investigational Product (IP) Manual.

5.1.5. Study Drug Preparation

IP is infused undiluted after pooling the contents of the calculated number of vials in an empty infusion bag according to the Dose Preparation Instructions in the IP Manual.

Once prepared, the IP for infusion is stable at room temperature for up to 6 hours. However, if prepared IP is stored refrigerated at 2°C to 8°C, the IP is stable for **48 hours**.

IP is administered by IV infusion, using an infusion set with a **0.2 µm in-line filter**.

5.1.6. Study Drug Administration

Dosing is based on the weight obtained on Day 1 and every 12-weeks thereafter. The total dose **is not to exceed 4.1g**. The total **volume of fluid is not to exceed 410 mL**. Study Drug is administered by IV infusion, using an infusion set with a sterile, nonpyrogenic, low-protein-

binding in-line filter (0.2-micron pore size). The infusion and post-infusion observation periods are provided in Table 1 below.

Table 1 Pamrevlumab (or placebo): Dose, Route, and Administration

Agent	Dose	Route	Infusion Rate	Frequency
Pamrevlumab/ matching placebo	30 mg/kg	IV	
 • First Infusion (including first infusion in OLE) : Infuse over approximately 2 hours. • Second Infusion (including second infusion in OLE): If first infusion is well tolerated, infuse over approximately 1 hour. • Subsequent Infusions: If 1 hour infusion(s) are well tolerated, infuse over approximately 30 minutes. 
For ALL infusions: A Post-infusion observation period has to be included throughout the study: It is 1 hour for at least the first 3 infusions (including in OLE); this may be reduced to 30 minutes if there were no infusion-related AEs after the first 3 infusions.
 
For Czech Republic only: A Post-infusion observation period has to be included throughout the study: 2 hours for the first 3 infusions; this may be reduced to 30 minutes if there were no infusion-related AEs after the first 3 infusions
	
Day 1 and Every 3 weeks thereafter
 
NOTE: Infusions must be AT LEAST 10 days apart

NOTE: DO NOT ADMINISTER STUDY DRUG AS AN IV PUSH OR BOLUS INJECTION, OR CONCURRENTLY IN THE IV LINE WITH OTHER AGENTS.

The first infusion should be completed in approximately 2 hours. If the first infusion is well tolerated and no infusion-associated AEs are observed during the infusion and observation period, the second infusion should be completed in approximately 1 hour. The subsequent infusion periods may be shortened to approximately 30 minutes, if no infusion-associated AEs were observed during the initial two infusions.

If an infusion-associated AE occurs during any of the subsequent infusions, study drug will be administered over approximately 1 hour for the next three infusions. If no infusion associated AEs are observed in any of these three infusions, the infusion may be decreased again to approximately 30 minutes.

The Investigator or other qualified personnel must be either present, or immediately available, during all infusions and observation periods for each subject. If a subject has a significant infusion associated AE, the infusion rate may be slowed or temporarily stopped, depending on the severity of symptoms. If such a subject continues study drug dosing, a physician should be immediately available during all subsequent infusions and observation periods at the site.

Subjects who experience an infusion associated AE will not be allowed to participate in Home Health Care (HHC). In addition, if a subject experiences a life-threatening (per Section 7.3.3) infusion-associated AE, study drug treatment must be permanently discontinued (see [Section 4.3](#)).

The Investigator has the option to use premedication, e.g., antihistamines, nonsteroidal anti-inflammatory drugs (NSAIDs) for a subsequent infusion: this may be discussed with the FibroGen Medical Monitor or designee.

Infusions are to be continued until the total volume has been administered. Subjects will remain at the study site for 1 hour (2 hours for Czech Republic Only) after the end of the infusion for clinical observation. This post-infusion observation period may be reduced to 30 minutes if the subject has had no infusion-associated AEs during the first three infusions.

Study drug will be administered at a hospital or ambulatory setting with adequate facilities for managing medical emergencies. Medications for the treatment of acute reactions, including anaphylaxis, must be available to study site staff for immediate use. There is no specific treatment for a pamrevlumab overdose or infusion-associated AEs. Signs and symptoms should be managed with appropriate standard of care treatment.

The Sponsor may consider the use of properly trained home health care staff to administer the infusions of study drugs at the subject's home and corresponding study assessments during the conduct of the study (after the completion of at least three 30-minute infusions without safety concerns), consistent with institutional regulations and policies. See Section 5.1.7 for details.

COVID-19 Vaccine and Study Drug Administration

If a subject receives a COVID-19 vaccine during the study, it is recommended that a time separation of at least 48 hours is maintained between administration of the COVID-19 vaccine (single/multiple dose) and study drug infusion. The time separation may allow for better interpretation of any adverse events and their relationship to the vaccine or study drug.

The following procedures must be performed prior to each infusion:

- Vital signs (blood pressure [BP], pulse, and temperature) within 30 minutes before starting the infusion
- Query subject and assess AEs and SAEs
- Record concomitant medications

The following procedures must be performed after each infusion:

- Vital signs (BP, pulse, and temperature) within 30 minutes after completion of the infusion
- Query subject and assess AEs and SAE's

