Each subject will receive pamrevlumab (30 mg/kg) every 3 weeks, using the weight obtained on Day 1 of the OLE phase (=EX Day 1), and every 24 weeks thereafter, for assessment of the proper weight-based dosing regimen. EX Day 1 is expected to be scheduled 3 weeks \pm 7 days after the Week 48 visit of the main study.

See Protocol Section 5 for detailed information on study drug infusions. Home infusions via home health care (HHC) may be available during the OLE phase of the study at the discretion of the Investigator but such home infusions services will not be reimbursed by the Sponsor. Any home infusions via home health care are not permitted until at least three infusions in the OLE period have been administered without safety concerns.

Subjects who experience a significant infusion-associated AE may not receive HHC. In addition, if a new safety concern arises during a home infusion, the subject has to attend an on-site visit for an Investigator assessment as soon as feasible.

Medications and supplies to treat suspected hypersensitivity/anaphylactic reactions must be available for immediate use for all study drug infusion visits.

Important NOTE: The infusion durations and post-infusion observations periods have to be followed per Table 1 in Protocol Section 5.1.6, including the initial dosing and observations periods. This is to ensure that subjects transitioning from placebo (in the double blinded phase) receive adequate safety monitoring during OLE.

Visit windows are within ± 7 days of the scheduled visit date from OLE (EX) Week 3 through last dose in the OLE; however, visits should be at least 10 days apart, to ensure intervals of at least 10 days between study drug infusions.

All study visits will be performed in accordance with the OLE Schedule of Assessments (SOA) presented in Appendix 6.

Missed Visits/Missed Doses

Scheduled visit dates are determined from the time of the first dose in OLE, which is defined as EX Day 1. If a subject misses a visit, the subject should resume the regular visit schedule at the next scheduled visit.

Missed doses are not to be made up through extra visits. If a subject misses more than two infusions in any 18-week period, or two sequential infusions, the FibroGen Medical Monitor should be notified. The reason for missed doses must be documented in the subject's clinical record.

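### Table 1 and the text of Protocol Section 5.1.6 set different conditions for shortening the infusion, so a subject with an early infusion-associated AE still judged well tolerated satisfies one and not the other

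*Protocol*

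**What the plan says.** Protocol Section 5.1.6 covers infusion duration twice.

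- **Table 1.** The first infusion takes about 2 hours. For the second: "If first infusion is well tolerated, infuse over approximately 1 hour". For later infusions: "If 1 hour infusion(s) are well tolerated, infuse over approximately 30 minutes". The table contains no rule for slowing down after a reaction or for returning to the shorter duration.
- **Text below Table 1, second infusion.** The 1-hour duration carries a double condition: "If the first infusion is well tolerated and no infusion-associated AEs are observed during the infusion and observation period".
- **Text below Table 1, later infusions.** "The subsequent infusion periods may be shortened to approximately 30 minutes, if no infusion-associated AEs were observed during the initial two infusions".
- **Text below Table 1, after a reaction.** The trigger is "If an infusion-associated AE occurs during any of the subsequent infusions". In that case "study drug will be administered over approximately 1 hour for the next three infusions". The way back is: "If no infusion associated AEs are observed in any of these three infusions, the infusion may be decreased again to approximately 30 minutes".

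For the open-label extension (OLE), the Important NOTE in Protocol Appendix 6 says that infusion durations and "post-infusion observations periods have to be followed per Table 1 in Protocol Section 5.1.6". A little earlier, the same part of Appendix 6 refers the reader generally to Protocol Section 5 for details of infusions.

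**The concern.** Two passages of one section govern the same decision with different tests. Table 1 asks whether the 1-hour infusion or infusions were tolerated. The text asks whether the first two infusions were free of infusion-associated AEs. The force differs too: the table instructs, while the text allows.

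Nothing in Section 5.1.6 says which prevails. With approximately 170 sites planned, some may work from the table and others from the paragraph, and would then infuse the same kind of subject over different durations. The subjects affected are those who have already had an infusion-associated AE. Hypersensitivity and anaphylactic reactions are a named safety assessment in Protocol Section 3.2.4, and SAP (double-blind period) Section 6.8.2 tabulates infusion reactions. Part of the variation in those tables could therefore come from which part of Section 5.1.6 a site followed.

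**Working it through.** The plan gives no figure to reproduce here, and no sample size, power or alpha is involved. The check is to trace both rules infusion by infusion.

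**Are the two terms interchangeable?** No. For infusion 2 the text requires good tolerance and, in addition, no infusion-associated AE. An infusion can therefore be well tolerated and still have an AE. Section 5.1.6 does not define good tolerance.

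**Tracing the rules (main phase, up to 17 infusions):**

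| Pattern | Table 1 | Text below Table 1 |
|---|---|---|
| No AE | 2 h, 1 h, then 30 min from infusion 3 | 2 h, 1 h, then 30 min allowed from infusion 3 |
| AE at infusion 1, judged well tolerated; infusion 2 tolerated and AE-free | 1 h at infusion 2; 30 min from infusion 3 | 1-hour condition not met at infusion 2; 30-minute condition not met from infusion 3; no route stated |
| AE at infusion 2 (given over 1 h), judged well tolerated | 30 min from infusion 3 | 30-minute condition not met from infusion 3; no route stated |
| AE at infusion 1, not well tolerated | 1-hour condition not met at infusion 2; no duration stated | 1-hour condition not met at infusion 2; no duration stated |
| AE at infusion 3 or later | Silent on slowing down and returning | 1 h for the next three infusions; 30 min possible again if all three are AE-free |

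The rules agree when there is no AE. They give different answers in the second and third rows. In the last row the text supplies a rule and the table has none.

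**Why the return path does not reach the early reactor.** In the text, the later infusions are those after the initial two. The slow-down rule is triggered by an AE in one of those and ends by going back to 30 minutes, which presupposes that the subject had already reached 30 minutes. An AE at infusion 1 or 2 is outside that wording unless the subject has a further AE at infusion 3 or later.

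**Size for one subject.**

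- Infusions at issue in the second and third rows: 17 − 2 = 15 (infusions 3 to 17), at most.
- Volume at 30 mg/kg (Table 1) and 10 mg/mL (Protocol Section 5.1.2), for an assumed weight of 70 kg: 70 × 30 / 10 = 210 mL.
- Rate: 210 mL / 1 h = 210 mL/h, against 210 mL / 0.5 h = 420 mL/h.
- At the 410 mL volume cap in Section 5.1.6: 410 mL/h against 820 mL/h.

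The ratio is 2 at any weight, because it only reflects 60 minutes against 30.

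**The case against.** The strongest reply is that table and text can be followed together, and that the conflict is narrower than it looks. Much of this stands.

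- **A reader might infer that Table 1 speeds up anyone who reacts early.** It does not. Its step to 1 hour requires the first infusion to have been well tolerated, so a subject who did not tolerate infusion 1 meets neither the table's condition nor the text's. The divergence needs an AE that was still judged well tolerated, and the count of 15 infusions carries the same condition.
- **A reader might infer that Table 1 asks for one clean 1-hour infusion after a late reaction where the text asks for three.** The table is silent there, and the text fills the gap in mandatory terms. A site can obey both, since the table's wording allows for more than one 1-hour infusion.
- **A reader might infer that the text bars an early reactor from 30 minutes.** It states no route, but it states no prohibition either.
- **A reader might infer that the OLE drops the slow-down rule because its note names Table 1.** The general reference to Protocol Section 5 brings the text in as well. What remains is that the specific citation points to the part of Section 5.1.6 without that rule.
- **A reader might infer that infusion duration is the main tool for handling reactions.** Section 5.1.6 also provides for slowing or pausing the infusion, premedication, a physician immediately available at later infusions after a significant AE, emergency medication on hand, exclusion from home infusion, and permanent discontinuation after a life-threatening AE.

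The main phase is also double-blind, so a site's reading is not tied to a known treatment arm. None of these points removes the difference in trigger or supplies the missing route for an AE at infusion 1 or 2.

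**Conclusion.** The concern holds in a limited form: Section 5.1.6 contains two stated conditions for the same step, and they give different answers for a subject whose AE at infusion 1 or 2 was judged well tolerated. The same mismatch applies to the step to 1 hour at infusion 2. The text's return rule does not address that subject, and Table 1 does not mention the rule at all.

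This rests on two readings: that an infusion with a mild AE can count as well tolerated, which the text's own double condition supports, and that a single 1-hour infusion satisfies Table 1, which fits the AE-free schedule, where infusion 2 is the only 1-hour infusion.

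Per subject, the size is a twofold difference in rate over at most 15 of 17 main-phase infusions. Across the trial it cannot be stated, because the documents give no infusion-reaction rate; Protocol Section 2.5 describes infusions as well tolerated to date, so few subjects may be affected. The consequence is for consistent conduct and safety handling. It changes no efficacy result, power or alpha. The correction is worth making because it concerns subjects who have already reacted and costs almost nothing.

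**What to change.** Reconcile Table 1 with the text below it so that one trigger term and one condition govern moving to the shorter infusion and returning to it. The reconciled rule should say what applies after an AE at infusion 1, at infusion 2, and at any later infusion, and should cover the step to 1 hour as well as the step to 30 minutes. Refer to that same rule, rather than to Table 1 alone, in the Important NOTE and the schedule footnote on infusions in Appendix 6. Which condition stands is for the sponsor's medical team; this review takes no view.

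The cost is the wording of one table cell and one paragraph, plus the cross-references in Appendix 6. Depending on the rule chosen, infusion time may be longer for some subjects who react.
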